
relevant as according to regulatory guidance, the QTc response should be characterised at a sufficiently high multiple of the clinically relevant exposure. In addition, considering the predicted maximum systemic exposure and the observed maximum individual AUC_{0-24h} at 6 mg in Part A, the highest dose is estimated to be 17 mg (Table 6). Regardless of this estimate, the highest dose will be determined based on the review of the maximum AUC_{0-24h} value at the previous dose level; however, the maximum dose that will be administered in Part A will not exceed 24 mg, which is 2-fold the previous dose level.

6. **Table 5:** Doses for Part A, Groups A4 and A5, have been changed based on the same rationale as described for the changes in Section 3.5.
7. **Tables 4 and 6:** These tables have been added to present the observed and estimated human exposures at Day 1 and steady state.
8. **Section 3.7:** The PK dose escalation stopping criterion that capped mean systemic exposure levels at a C_{max} of 179 ng/mL and/or AUC_{0-24h} of 988 ng·h/mL has been removed based on the same rationale as described for the changes in Section 3.5. The PK dose escalation stopping criterion for individual systemic exposure levels has not been removed.
9. **Section 5.1:** The United Kingdom is no longer part of the European Union, so the Qualified Person in the European Union is now described as a Qualified Person in the United Kingdom.
10. **Table 7:** Doses for Part A, Groups A4 and A5, have been changed and therefore, the number of 1 and 10 mg KRP-A218 and placebo tablets have been updated to reflect the change in dose levels.
11. **Section 9:** The reference list has been updated with new references due to the new information added into Section 3.5.

Minor Changes:

1. **Throughout document:** Numbers have replaced Roman numerals when describing the phase of a study within the protocol body and synopsis. No change has been made to the study title.
2. **Synopsis:** Updated to reflect changes in the protocol body, as applicable.
3. Due to rebranding of Covance to Labcorp Drug Development, updates throughout the protocol have been made, as appropriate.
4. The amendment/version number and date were updated throughout the protocol.
5. Minor editorial changes.

Version 3.0 to Version 4.0

This nonsubstantial amendment has been issued to make the following changes:

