B4	0231 – 0240	8 KRP-A218 2 placebo	X mg	Fasted/Fed ^b	Male	
Part C	C1	0301 – 0312	12 KRP-A218 (2 doses)	X mg	Fasted/Fed ^b	Male

^a Female subjects in Group A2b will participate in Treatment Period 1 only. Male subjects in Group A2a will be administered the same treatment in both treatment periods and will be in the fasted state in Treatment Period 1 and in the fed state in Treatment Period 2.

^b The dietary state for dosing will be determined by comparing the PK data between the fed and fasted state in Group A2a.

For Part A, the planned first dose level is 1 mg. The dose level of the subsequent group will be set so that the predicted mean exposure does not exceed 5-fold the mean exposure of the previous group for predicted nonpharmacologically active dose, and 2-fold the mean exposure of the previous group for predicted pharmacologically active dose. The highest dose level will be guided by the review of safety, tolerability, and PK data from prior dose levels. In each group in Part A, predicted maximum systemic exposure (C_{max} and AUC_{0-24h}) of **CCI** in individual subjects will not exceed a C_{max} of 1220 ng/mL and/or an AUC_{0-24h} of 3930 ng·h/mL; i.e., systemic exposure will not exceed that seen in the male rat, which was the lowest systemic exposure that was seen at either 5 mg/kg/day in rats or the NOAEL of 2 mg/kg/day in dogs. Considering the predicted maximum systemic exposure and the observed maximum individual AUC_{0-24h} at 6 mg in Part A, the highest dose is estimated to be 17 mg (Table 6). Regardless of this estimate, the highest dose will be determined based on the review of the maximum AUC_{0-24h} value at the previous dose level; however, the maximum dose that will be administered in Part A will not exceed 24 mg, which is 2-fold the previous dose level.

Table 6: Estimated Human Exposure at Day 1

Dose (mg)	C_{max} (ng/mL)		AUC_{0-24h} (ng·h/mL)	
	Mean	Maximum	Mean	Maximum
6	60.3	95.7	813	1350
12*	121	191	1630	2700
17*	171	271	2300	3830

* C_{max} and AUC_{0-24h} were calculated based on geometric mean parameter values from 6 mg KRP-A218 in Part A, assuming linearity across dose.

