3.6. Dose Escalation

Doses will be administered in an escalating manner following satisfactory review by the Sponsor, Investigator, and Labcorp Drug Development Medical Monitor of the safety and tolerability data (up to 48 hours post last dose) and plasma PK data (up to 24 hours post last dose) from the previous lower dose level. Doses may be reduced and may be lower than the starting dose. There will be a minimum of 6 days between dose escalations to allow sufficient time for an adequate safety review.

Dose escalation in both Parts A and B will only occur if data from a minimum of 6 subjects have been reviewed from the previous lower dose group, such that data from a minimum of 4 subjects who have received KRP-A218 will be used to make the dose escalation decision.

The justification for this is as follows:

- Based upon nonclinical data, no clinically important off-target effects are expected within the proposed dose range.
- A minimum of 4 subjects receiving the active drug is considered sufficient to characterise the safety profile and PK response to KRP-A218.

Between each dose escalation, the Investigator will review all available data in a blinded manner to ensure it is safe to proceed with the planned dose escalation. An interim safety report, summarising results from all available safety assessments, will be sent to the Sponsor and Labcorp Drug Development Medical Monitor prior to the start of each successive group. Any clinically significant results will be discussed with the Sponsor before dose escalation continues. Interim PK data will also be reviewed in terms of dose escalation and to confirm that the study design remains appropriate. In the event of a disagreement between Sponsor and Investigator on the dose escalation decision, the decision of the Investigator will be upheld.

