3.7. Dose Escalation Stopping Criteria

The study will be halted if 1 or more subjects experience an SAE that is considered to be related to IMP or 2 or more subjects in the same group experience severe AEs that are

considered to be related to IMP. If, following an internal safety review, the Sponsor deems it appropriate to restart the study, this can be done following approval of a substantial protocol amendment.

For both Parts A and B, a consultation between the Investigator, Sponsor, and Labcorp Drug Development Medical Monitor will be held prior to dosing the next group. Dose escalation will stop if:

- Clinically relevant signs or symptoms of similar nature occur in 2 or more subjects in a group that, in the opinion of the Investigator, warrant stopping of dose escalation. In particular, the Investigator (or designee) should carefully monitor signs or symptoms below:
 - symptoms such as inappetence, abdominal distension, abdominal discomfort, abdominal pain, nausea and vomiting
 - signs/findings such as abdominal tenderness and decreased or absent peristaltic sounds
 - abnormal faeces such as diarrhea, hematochezia, and melena.
- Inappetence, abdominal distension, abdominal discomfort, abdominal pain, nausea and vomiting that prevent subjects from eating a meal on 3 or more occasions on 2 consecutive days in 1 or more subjects in a group.
- Diarrhea, defined as 7 or more episodes, rated as ≥ 5 on the Bristol Stool Chart, in 1 day for 2 consecutive days in 1 or more subjects in a group.
- Hematochezia and melena with visible blood that are considered to be caused by gastrointestinal bleeding in 1 or more subjects in a group.
- Clinically significant increases in liver function tests compared to baseline measurements, defined as AST, ALT, ALP, and/or γ -GTP $\geq 3 \times$ the upper limit of normal (ULN) and/or T-Bil $\geq 2 \times$ ULN (confirmed with repeat testing) in 2 or more subjects in a group.
- Maximum systemic exposure level of CCI [REDACTED] in individual subjects in the next group predicted to exceed a C_{max} of 1220 ng/mL and/or an AUC_{0-24h} of 3930 ng \cdot h/mL.

The dosing status of an individual subject may be unblinded to reviewers of the safety data if necessary for safety reasons or if pertinent to dose escalation decisions. The unblinded status will be kept to a minimum number of reviewers, based on pertinence to their role and relevant task. Further information on blinding can be found in [Section 5.4](#).

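### Section 3.5 says individual exposure will stay below the male-rat value, but its only worked prediction scales one observed maximum with no margin, and the next group's largest value exceeds such a prediction about half the time

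*Protocol*

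**What the plan says.** Protocol section 3.5 sets the limit for Part A on a prediction: the predicted maximum systemic exposure "in individual subjects will not exceed a C_{max} of 1220 ng/mL and/or an AUC_{0-24h} of 3930 ng·h/mL". The same sentence then glosses this without the word predicted: "systemic exposure will not exceed that seen in the male rat, which was the lowest systemic exposure". Earlier in 3.5 the rat values are presented as the ceiling for individuals. The text on Parts B and C repeats both the limit and the gloss.

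On the top Part A dose, section 3.5 estimates 17 mg from the largest individual AUC0-24h at 6 mg (Table 6). It then says that "the highest dose will be determined based on the review of the maximum" AUC0-24h at the previous dose level, subject to a 24 mg ceiling. It also keeps a step limit of 2-fold on predicted mean exposure at pharmacologically active doses.

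Section 3.7 stops escalation when the maximum level "in individual subjects in the next group predicted to exceed a C_{max} of 1220 ng/mL" or the AUC value. Section 3.6 lets a decision go ahead when "data from a minimum of 4 subjects who have received KRP-A218 will be used".

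Section 3.5 further assumes, from the individual values in Groups A1 to A3, that the maximum AUC0-24h may be about twice the mean. Neither the protocol nor the SAP defines how a predicted maximum is to be computed or what margin it carries.

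**The concern.** The largest value among 4 to 6 subjects is not an upper limit for 6 new subjects. Multiplying it by the dose ratio carries it to the next dose but adds nothing for sampling variation. The statistic also runs the wrong way: the fewer subjects reviewed, the smaller the observed maximum tends to be, and the higher the dose that appears to respect the limit.

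At stake is a stated assurance to healthy subjects, and to those who approve the protocol, about individual exposure. A reader of 3.5 would take it that no subject will go above the rat exposure. A prediction with roughly even odds of being exceeded cannot support that. The wording carries over to 14-day dosing in Part B and to the itraconazole part.

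**Working it through.** **Inputs.** Table 6, 6 mg row: mean AUC0-24h 813, maximum 1350; mean Cmax 60.3, maximum 95.7. Limits: AUC0-24h 3930, Cmax 1220 (sections 3.5 and 3.7). Active subjects per Part A group: 6 (section 3.1.1); minimum reviewed: 4 (section 3.6). AUC0-24h CV in the fasted groups: 19.5% (1 mg), 21.4% (3 mg), 27.9% (6 mg) (Table 3). Assumptions: exposure linear in dose (as in Table 6), exchangeable subjects, log-normal values, and the tabulated CV read as a geometric CV, so log SD = √ln(1 + CV²) = 0.193, 0.212 and 0.274.

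**1. Reproducing Table 6.**
- Highest dose: 6 × 3930/1350 = 17.5, so 17 mg.
- Maximum at 12 mg: 1350 × 12/6 = 2700. At 17 mg: 1350 × 17/6 = 3825 (printed 3830).
- Mean at 17 mg: 813 × 17/6 = 2304 (printed 2300).
- Maximum Cmax at 17 mg: 95.7 × 17/6 = 271, far below 1220, so AUC is the binding limit.

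The maximum column is therefore one observed value times the dose ratio.

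**2. How often such a prediction is exceeded.** If dose-normalised values are exchangeable, the overall largest of n1 old and n2 new values is equally likely to be any of them:

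P(new maximum > scaled old maximum) = n2/(n1 + n2)

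- 6 reviewed, 6 new: 6/12 = 50%.
- 4 reviewed, 6 new: 6/10 = 60%.

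This holds for any continuous distribution and any CV.

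**3. If Group A5 were dosed at the limit by the same scaling.** Dose = min(24, 12 × 3930/maximum at 12 mg), with a mean at 12 mg of 813 × 2 = 1626. Simulated probability (500,000 runs) that at least one of 6 subjects exceeds 3930:

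| CV | 6 reviewed, exact dose | 6 reviewed, whole mg | 4 reviewed, exact dose | 4 reviewed, whole mg |
|---|---|---|---|---|
| 19.5% | 44% | 41% | 50% | 47% |
| 21.4% | 46% | 42% | 52% | 49% |
| 27.9% | 48% | 45% | 56% | 53% |

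At CV 27.9%, reviewing 4 rather than 6 raises the median resulting dose from 20.7 to 22.1 mg, which shows the perverse direction.

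**4. At the 17 mg estimate.** With p = P(Z > ln(3930/2304)/log SD) per subject, the chance for any of 6 is 1 − (1 − p)⁶.
- CV 27.9%: z = 1.95, p = 0.0255, any of 6 = 14.4%.
- CV 21.4%: z = 2.52, p = 0.0058, any of 6 = 3.4%.
- CV 19.5%: z = 2.76, p = 0.0028, any of 6 = 1.7%.

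At CV 27.9%, treating the mean and SD as estimated from 6 subjects gives about 27%. These figures are lower than in step 3 because the 6 mg maximum was a high draw: 1350/813 = 1.66 times the mean.

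**5. The two predictors in section 3.5.** Twice the 17 mg mean is 2 × 2300 = 4600, above 3930. Table 6 gives 3830, below it. The section supports both answers for the same dose.

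**6. Do the other limits secure the individual one?** Going from 12 to 24 mg satisfies both the 2-fold mean step and the 24 mg ceiling. The mean would then be 813 × 4 = 3252. The chance that any of 6 exceeds 3930 would be 66% (CV 19.5%: z = 0.98, p = 0.163) to 81% (CV 27.9%: z = 0.69, p = 0.245).

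**The case against.** The strongest reply is that the operative limit is on predicted exposure in both 3.5 and 3.7, so an actual value above 3930 breaches nothing. This is right about the criterion. It does not rescue the gloss ("systemic exposure will not exceed that seen in the male rat") or the description of the rat values as the ceiling for individuals, and these are what a reader will rely on.

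Second, the documents do not say that Group A5 will be dosed at the limit by scaling. They speak of a review of the maximum, guided by all safety, tolerability and PK data. That stands: step 3 is conditional on an inference from Table 6. Still, no other prediction method is shown.

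Third, the 4-subject case is only a permitted minimum. Section 1.3 reports that all 8 subjects in Group A3 were reviewed. It also reports that 6 of the 8 in Group A2a were, so partial review does occur.

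Three stronger readings are tempting and not supported:
- That a Group A5 subject will exceed the limit with about even odds whatever is chosen. The 40-56% applies only to a dose set at the limit, before the 12 mg data are seen; at 17 mg the figures are much lower.
- That the individual cap is the only PK limit left on escalation. Section 3.5 keeps the 2-fold step on mean exposure and the 24 mg ceiling.
- That the 66-81% at 24 mg is the risk of the plan. By the scaling, 24 mg is reached only if the 12 mg maximum is at most 3930 × 12/24 = 1965, which is 1965/1626 = 1.21 times the expected mean.

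Nor is exceeding a rat-exposure limit shown to be harm in itself.

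**Conclusion.** The assurance in section 3.5 is wrong as written: the method shown does not deliver it. A scaled sample maximum is exceeded by the next group's largest value with probability 50% (6 active subjects reviewed) or 60% (4 reviewed), given only linearity and exchangeable subjects; a more than proportional rise in exposure would increase this.

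The probability of exceeding 3930 depends on the dose chosen. It is about 40-56% if the dose is placed at the limit by the same scaling, and at 17 mg about 2-14% with the mean and CV taken as known, or about 27% at the 6 mg CV when they are treated as estimated. These figures rest on log-normality, the Table 3 CVs and the 6 mg mean.

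Separately, the 2-fold assumption and Table 6 contradict each other at 17 mg (about 4600 against 3830), and the passages must be reconciled. The defect lies in the assurance and the undefined prediction. It does not show that any particular dose or cap is wrong.

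**What to change.** - In 3.5 (Parts A, B and C) and 3.7, state consistently that the limit applies to predicted exposure, and say how the predicted maximum is obtained.
- Remove or qualify the gloss that exposure will stay below the male-rat value, and the description of the rat values as the ceiling for individuals.
- Reconcile Table 6 with the assumption that the maximum is about twice the mean, so that the section gives one answer for one dose.
- At each escalation review, report the probability that any subject in the next group exceeds the limit, computed from the between-subject variability pooled over the completed groups.

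No dose, cap, acceptable probability or escalation rule is proposed; those stay with the existing reviewers.

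The cost is a wording change in two sections and a short calculation per review on data already in hand. The downside is that the stated assurance becomes less favourable.

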EDC	electronic data capture
FSH	follicle-stimulating hormone
HDL-C	high-density lipoprotein cholesterol

HED	human equivalent dose
hERG	human ether-a-go-go-related gene
HRV	human rhinovirus
Ht	hematocrit
IB	Investigator's Brochure
I-Bil	indirect bilirubin
IC ₅₀	concentration producing 50% inhibition
ICF	informed consent form
ICH	International Council for/Conference on Harmonisation
IMP	investigational medicinal product
ITCZ	Itraconazole
IUD	intrauterine device
K	Potassium
LDH	lactate dehydrogenase
LDL-C	low-density lipoprotein cholesterol
MCH	mean cell haemoglobin
MCHC	mean cell haemoglobin concentration
MCV	mean cell volume
MRSD	maximum recommended starting dose
Na	sodium
NOAEL	no observed adverse effect level
P	inorganic phosphate
PI4K	phosphatidylinositol 4 kinase
PI4K2A	phosphatidylinositol 4 kinase type 2α
PI4K2B	phosphatidylinositol 4 kinase type 2β
PI4KB	phosphatidylinositol 4 kinase IIIβ
PK	pharmacokinetic(s)
PL	Phospholipid
PLT	Platelet
PT-INR	prothrombin time/international normalised ratio
QD	quaque die (once-daily)
QTcF	QT interval corrected for heart rate using Fridericia's method
AR _{AUC0-τ}	observed accumulation ratio based on AUC _{0-τ}
AR _{C_{max}}	observed accumulation ratio based on C _{max} during the dosing interval
RBC	red blood cell
SAE	serious adverse event
t _{1/2}	apparent terminal elimination half-life
T-Bil	total bilirubin
T-CHO	total cholesterol
TG	Triglycerides

t_{max}	time of the maximum observed concentration
TMF	Trial Master File
TP	total protein
UA	uric acid
ULN	upper limit of normal
V_z/F	apparent volume of distribution
WBC	white blood cell
γ -GTP	gamma-glutamyl transferase

1. INTRODUCTION

1.1. Background

KRP-A218 is a novel orally active antiviral agent for positive-strand ribonucleic acid (RNA) viruses, discovered and synthesized by Kyorin Pharmaceuticals Co. Ltd., Japan, for the indication of human rhinovirus (HRV) infection. KRP-A218 is an adenosine triphosphate (ATP)-competitive and subtype specific inhibitor for phosphatidylinositol 4-kinase beta (PI4KB), known as a host cell factor required for the viral replication of HRVs and enteroviruses (EVs). KRP-A218 shows broad-spectrum antiviral activity against HRVs and EVs by PI4KB inhibition.

HRVs and EVs belong to the *Picornaviridae* family and they have been clustered into 7 groups: RV-A, B, C and EV-A, B, C, D.^[1] HRV has more than 100 serotypes, which are highly prevalent respiratory pathogens traditionally associated with mild and self-limited upper respiratory tract infections (URTI; ‘common cold’), and is the most commonly isolated virus as a causative virus for URTI.^[2] Furthermore, HRV is known to cause more severe diseases of lower respiratory tract such as pneumonia and bronchiolitis in immunocompromised patients, infants, children, and elderly, and exacerbation of chronic respiratory diseases including asthma, chronic obstructive pulmonary disease (COPD), interstitial lung disease, and cystic fibrosis.^[3, 4, 5] Especially, in immunocompromised patients such as hematopoietic cell transplantation (HCT) recipients and hematological malignancy patients, HRV is considered to be an important virus because HRV infection is not limited to URTI, it may progress to lower respiratory tract infection (LRTI) and cause death.^[6, 7] Among immunocompromised patients, HCT recipients are the most studied about severity risk of HRV infection.^[7, 8] The incidence of URTI by HRVs of HCT recipients is 22 to 25%^[9, 10], and median duration of viral shedding was 3 weeks (prolonged shedding of at least 3 months occurred in 6 of 45 patients). The rate of progression to LRTIs is 17 to 32%.^[11, 12, 13] The mortality rate is 41% when it deteriorates in LRTI.^[7] Enterovirus also has more than 100 serotypes, and most infected people only have mild illness, like the common cold, hand-foot-mouth disease, and conjunctivitis. However, in infants, children, and people with decreased immunity, EV causes severe diseases including paralytic disease, meningitis, encephalitis and myocarditis.^[14, 15] Currently, there are no approved antiviral agents for treatment of HRV and EV infection and efforts at vaccine development are hindered by the existence of more than 100 HRV and EV serotypes with high level sequence variability in the antigenic sites. In addition, the genetic variability within the HRV or EV species necessitates the development of broad-spectrum, pan HRV or EV antiviral drugs. Therefore, there is an unmet medical need for HRV and EV infection in the patients with risk to progress severe condition by those infections.

This first-in-human study has 2 purposes. One is to evaluate the safety, tolerability, and pharmacokinetics (PK) of CCI (the active ingredient in KRP-A218), and the other is to evaluate a drug-drug interaction (DDI). The PK of CCI will be evaluated following administration of single and multiple doses of KRP-A218. In the DDI study, the effect of co-administration of itraconazole on the PK of CCI will be evaluated, since the nonclinical study data suggested that CCI is a Cytochrome P450 (CYP) 3A4 substrate. Itraconazole has been chosen as it is recommended by the European Medicines Agency (EMA) [16] and the Food and Drug Administration (FDA) [17] as a suitable potent CYP3A4 inhibitor for use in DDI studies.

1.2. Nonclinical Development

The compound codes used throughout this section are presented below.

Drug Substance Codes	Description
CCI [REDACTED]	Drug substance of KRP-A218
CCI [REDACTED]	Active ingredient

The nonclinical program supporting initial clinical administration of KRP-A218 comprises a set of nonclinical pharmacology, safety pharmacology, absorption, distribution, metabolism and excretion (ADME), and toxicology (general toxicity and genotoxicity) studies.

CCI [REDACTED] was found to be a highly potent (Inhibitory constant [Ki] value of 6.9 nmol/L), ATP-competitive, and a specific inhibitor of recombinant human PI4KB (50% inhibitory concentration [IC₅₀] value of 11 nmol/L, selectivity ratio for PI4KB over other phosphatidylinositol 4-kinases [PI4Ks] of ≥160), and demonstrated consistent potent and broad-spectrum antiviral activity against different HRV and EV serotypes (50% effective concentration [EC₅₀] values of 19 to 77 nmol/L). Primary pharmacology and ADME studies were performed with CCI [REDACTED], while dose levels for safety pharmacology and toxicology studies (including toxicokinetic interpretation) were calculated based on the free form of CCI [REDACTED]. In vivo pharmacology studies showed that CCI [REDACTED] suppressed viral infection in RV-A1B-infected corticosteroid-treated and coxsackievirus-B3 (CV-B3)-infected mouse models, with a minimum pharmacologically active oral dose of 1 mg/kg. In addition, CCI [REDACTED] improved the survival rate in CV-B3-infected mice even when initially dosed starting 48 hours after infection at dose of 3 and 10 mg/kg/day. CCI [REDACTED] was also effective against the viral load in lung of RV-A1B-infected mice at dose of 3 mg/kg and over.

Systemic exposure to CCI [REDACTED] following single or repeated oral dosing with CCI [REDACTED] was established in mouse, rat, dog, and monkey. There were no remarkable differences in exposure with repeated dosing and between the sexes, although values in females were slightly higher than in males for rats. Blood-plasma concentration ratio of CCI [REDACTED] was similar across mouse, rat, dog, monkey, and human, with values of 0.909, 1.03, 0.933, 1.80, and 1.10, respectively, while plasma protein binding was 85.8, 75.6, 82.7, 79.7, and 88.4% in mouse, rat, dog, monkey, and human, respectively. CCI [REDACTED] was metabolized by CYP3A, CYP2C9, CYP2C8, and CYP2D6. The contribution ratio for CCI [REDACTED] metabolism was determined as ranging from 68.4 to 94.4% for CYP3A and was determined as ranging from 5.7 to 22.0% for CYP2C9. CCI [REDACTED] generally had low potential for inhibition although slight time dependent inhibition was observed for CYP3A4 and it was shown to have a potential to induce CYP1A2, CYP2B6, CYP2C9, and CYP3A4.

A core battery of central nervous system, respiratory and cardiovascular (CVS) studies with CCI [REDACTED] showed no safety concerns. CCI [REDACTED] was shown to have no genotoxic potential from evaluation in a bacterial reverse mutation test, an in vitro chromosome aberrations assay in Chinese hamster lung cells and a bone marrow micronucleus study in rats. In a 2-week good laboratory practice (GLP) oral toxicology study in the rat, the no observed adverse effect level (NOAEL) of CCI [REDACTED] was considered to be below 5 mg/kg/day for males (based on inflammatory cell infiltration in the lumen of the coagulating gland) and 5 mg/kg/day for

females (based on an increase in total cholesterol [T-CHO] and emperipolesis in the bone marrow in both sexes at ≥ 10 mg/kg/day). In a 2-week GLP oral toxicology study in the dog, the NOAEL of CCI [REDACTED] was 2 mg/kg/day for both males and females, based on: abnormal stools, decreased bodyweight and decreased food consumption at ≥ 4 mg/kg/day; increased blood lipid system parameters (triglycerides, T-CHO, LDL-C, free cholesterol) and deviation enzymes at ≥ 4 mg/kg/day; and histopathological gastrointestinal (GI) changes in 1 female at 4 mg/kg/day (and 1 male and 1 female at 8 mg/kg/day), culminating in the death or early sacrifice of dogs given ≥ 6 mg/kg/day. In a non-pivotal 2-week toxicity study in male mice, the NOAEL of CCI [REDACTED] was 10 mg/kg/day, based on: decreased body weights, cumulative body weight gain, and food consumption at 300 mg/kg/day; increased blood lipid system parameters (T-CHO, HDL-C, LDL-C) at ≥ 30 mg/kg/day; and histopathological changes in the stomach and small intestine at 300 mg/kg/day, culminating in the death or early sacrifice of mice given 300 mg/kg/day.

Toxicokinetic parameters determined from the pivotal 2-week repeat dose studies in rats and dogs are presented in Table 1 and Table 2.

Table 1: Summary of Toxicokinetic Parameters in 2-week Toxicity Study in Rat Given CCI [REDACTED]

Dose level (mg/kg/day)	N (M/F)	Day	Male			Female		
			C _{max} (ng/mL)	T _{max} (h)	AUC _{0-24h} (ng·h/mL)	C _{max} (ng/mL)	T _{max} (h)	AUC _{0-24h} (ng·h/mL)
5	3/3	1	962	0.5	3610	1370	0.5	4910
	3/3	14	1220	0.5	3930	1600	0.5	4780
10	3/3	1	2130	1.0	8620	3220	0.5	12 500
	3/3	14	2010	1.0	8580	3490	0.5	10 700
20	3/3	1	4900	0.5	23 000	6220	0.5	30 200
	3/3	14	5110	0.5	20 900	7990	0.5	27 400
40	3/3	1	7960	0.5	51 600	9600	0.5	56 800
	3/3	14	8890	0.5	48 700	10 600	0.5	59 700

Mean (n = 3); AUC_{0-24h} = area under the concentration-time curve from time 0 to 24 hours; C_{max} = maximum concentration; T_{max} = time of maximum concentration; N (M/F): Number of animals (male/female)

Table 2: Summary of Toxicokinetic Parameters in 2-week Toxicity Study in Dog Given CCI [REDACTED]

Dose level (mg/kg/day)	N (M/F)	Day	Male			Female		
			C _{max} (ng/mL)	T _{max} (h)	AUC _{0-24h} (ng·h/mL)	C _{max} (ng/mL)	T _{max} (h)	AUC _{0-24h} (ng·h/mL)
2	3/3	1	1450	0.8	8020	918	1.3	6000
	3/3	14	1450	0.7	9340	1350	0.8	8500
4	3/3	1	2780	1.7	19 900	2420	1.3	15 000
	3/3	14	3520	0.7	29 400	3120	0.8	19 900
6	3/3	1	4010	1.2	30 500	3820	1.0	27 900
	3/3	14	4420	1.0	35 000	5100	1.2	48 800
8	3/3	1	4840	1.3	35 800	5850	1.1	41 300
	3/3	14	4390	1.5	38 200	3310	2.0	34 700

Mean (n = 3); AUC_{0-24h} = area under the concentration-time curve from time 0 to 24 hours; C_{max} = maximum concentration; T_{max} = time of maximum concentration; N (M/F): Number of animals (male/female)

